## 4.4. Primary Aim 4: To standardize and assess the role of "informed consent" in affecting the decision to donate and satisfaction after living liver donation.

- 962 The motivation(s) for a healthy individual to subject themselves to a potentially life
- 963 altering/threatening procedure is not clearly understood. Much of the current direction in Revised Cohort Protocol 031006 Page 23 of 56

964 disclosure of information about the donation process assumes that the potential donor 965 uses a contemplative risk/benefit analysis matrix to arrive at a decision to donate. Past 966 experience with kidney donors suggests that the contemplative risk/benefit analysis 967 applies only to a minority of donors. The majority of donors approached the donation 968 procedure because of a primary sense of duty. For the living liver donor, the primary 969 motivating forces of the potential donors are unknown. Of the people screened, it is our 970 hypothesis that certain personal characteristics (strong sense of duty or need to perform a 971 moral good) will be present in those individuals that go through to donation, as compared 972 to those individuals that enter the process but withdraw. Whether disclosed information 973 or life situations are the pivotal factors in altering the decision making process for 974 donation is unclear. It is not clear what type or amount of information would be required 975 to alter the desire to help another by the donation of an organ. A correlation between the 976 level of understanding and subsequent decision-making process would be desirable.

977 978

979 The informed consent process assumes that retention of information by the potential 980 donor will alter the acceptance of adverse events when they occur. The measurement of 981 the acceptance of disclosed vs. undisclosed adverse events is not certain for the 982 previously healthy individual. We hypothesize that the process of repetitive disclosure 983 (informed consent) of the possibility of specific adverse outcomes will make it "easier" 984 for the donor to accept the disclosed complication, rather than the complication which occurs at a relatively low frequency that was not included in the standardized informed 985 986 consent material. Whether donor satisfaction correlates with ease of donor course (as in 987 the standard surgical procedure) or with the more complex social matrix of recipient 988 health and family acceptance needs to be measured.

989

990 The use of healthy individuals as a source of organs for transplantation has always been 991 controversial. It goes against the basic Hippocratic tenet of "primum non nocere" to 992 subject a healthy person to a procedure that will produce no physical benefit. The 993 transplant community has argued that the psychological benefits to the donor will 994 outweigh the risks for the emotionally related individual. Family and social pressures 995 have often resulted in individuals stepping forward to the perceived aide of an 996 endangered loved one.

997

998 A living liver donor death in New York resulted in an intense scrutiny of the process of 999 donor evaluation, operative and perioperative care and informed consent. The Advisory 1000 Committee on Organ Transplantation (ACOT) to Secretary Thompson issued guidelines 1001 regarding the process and information given to the potential living donor. The first 1002 ethical principle is that the donor must be competent to make a decision. Competency is 1003 a word with multiple meanings in the legal and common usage. In the common usage, 1004 competency assumes a basic level of understanding of information and possession of 1005 enough cognitive skills to derive a reasonable conclusion. However, using the legal 1006 definitions of competency (and it is unclear how much of the informed consent disclosure 1007 is to meet legal standards, ethical standards vs. best practice standards) an individual can 1008 be competent and fail to "adequately" understand the disclosed information necessary to 1009 meet a "best practice standard".

#### 1011 **4.4.1. Study Methods**

1027

1012 All potential donors would be given a uniform amount of information regarding the 1013 donation process and the incumbent risks associated with donation. The information 1014 disclosure and ethical principles of this process will embrace the recommendations of the 1015 ACOT. In an attempt to standardize the presentation of the materials, collaboration with 1016 Keris, Inc. (Bellevue, WA) has resulted in the development of a standardized information 1017 disclosure that utilizes multimedia technology (the Vital Link Unit) for information 1018 presentation and data capture. Incorporated into the multimedia presentation are 1019 standardized tests to measure understanding and motivation. There are three presentations 1020 addressing the donor evaluation process, the donation surgery, and post-operative 1021 expectations. The scripts for these presentations are included as Appendices I-K. In 1022 addition to the standardized media presentations, each center will interact with the 1023 individual donors in their routine standard of practice. Attempts will be made to use the 1024 Vital Link Unit for information capture in the post-donation period, however if donors 1025 cannot access the transplant center's Vital Link, questionnaires will be mailed to attempt 1026 to capture motivation/satisfaction.

- 1028 Incorporated into the media presentation will be standardized assessment measures of:
- 1029 1. Comprehension and understanding: Understanding by the potential donor of the 1030 material will measured by the MacArthur Competency Assessment Tool-Clinical Research (MCAT-CR), Appendix L. This tool was developed over the past 1031 1032 decade to assess the capacity of an individual to enter into clinical research protocols. This tool was chosen rather than its therapeutic counterpart, after the 1033 1034 informed consent subcommittee discussed the observation that the individual had 1035 no direct health benefit from donation and that measures of understanding and appreciation of lack of personal benefit needed to be assessed. These were best 1036 accomplished through the MCAT-CR. The questions for this study have been 1037 1038 adapted by [name] (the primary author of the tool) into a format that 1039 can be captured through the audiovisual capture capacity of the Vital Link center. 1040 During the first visit to the transplant center (before going through the evaluation 1041 process) the individual will be asked questions, the answers will be recorded, 1042 stored at the DCC and reviewed in batches (at intervals to be determined) by the clinical psychologists at the University of Virginia. The responses will be scored 1043 1044 for understanding, appreciation and reasoning by previously established criteria. 1045 The scores of capacity for understanding, appreciation and reasoning other 1046 "normal" individuals will be available for comparison to those from the potential 1047 living donors.
- 1048 2. Motivation for decision-making: Donors are typically motivated by a sense of duty. Very little is known about the affect the information disclosure/evaluation 1049 1050 process upon the motivation of potential donors, either kidney, liver or lung organ 1051 donors or bone marrow donors. It is anticipated that the comprehensive, 1052 standardized disclosure of information that will be given to the potential living 1053 liver donor may change the person's motivation to proceed. To test whether there 1054 is a change in motivation, standardized questions about motivation to donate will be asked at the first encounter with the center (pre-information) and at the time of 1055 1056 donation (at the time of acquisition of informed consent for the operation). Ouestions will also be asked of those individuals that voluntarily withdraw from 1057 1058 the process, those individuals that were excluded from being a donor for

1059	discovered/medical reasons, and those whose prospective recipients either
1060	received a DDLT, were removed from the waiting list or died. The parameters of
1061	the questions are derived from previous studies in donors (kidney, bone marrow
1062	and lung). These questionnaires and a list of their measures are included as
1063	Appendices M-Q.

- 10643. Measures of quality of life: There are a variety of quality of life issues, but1065relevant to the informed consent process, assessment of anxiety/depression and1066physical perception/pain/function are key parameters. As these perceptions1067change with time after the donation, capture of this information at fixed time1068points after the procedure (3 and 12 months and yearly) will be done. It will be1069important to correlate the assessment of these measures to complications1070associated with either the donor operation or to the recipient.
- 1071 4. Measures of satisfaction.
- 1072

#### 1073 4.4.2. Participant Selection

- 1074 See Section 4. and Section 4.4.1.
- 1075

#### **4.4.3. Data Elements**

- 1077 These are listed above under Study Methods.
- 1078

1079

#### 4.4.4. Sample Size and Power Calculations

1080 The sample size for the first hypothesis on predictors of donation will include all 1081 potential donors in the Cohort Study, assumed to be 360 donors + 710 donor controls = 1082 1070 total. Based on logistic regression with significance level 0.05 and 2-sided tests, we 1083 will have 87% power to detect a difference between a 30% donation rate at the mean 1084 level of, say, the sense of duty scale, and a 35% donation one standard deviation above 1085 the mean. This assumes a correlation of only 0.05 between the variable of interest (e.g., 1086 sense of duty) and the control variables (e.g., demographics).

1087

1088 The sample size for the second hypothesis on satisfaction with treatment will include 1089 only those potential donors who actually donate, approximately 360 donors. Based on 1090 standard linear regression, we will have 93% power to detect an increase of 3% in the R-1091 squared value of the regression, assuming 5 control variables that explain a total of 10% 1092 of the variation. For the analysis of satisfaction with care at the evaluation time point, the 1093 sample size will be much larger since it will include all prospective donors and thus will 1094 have even more power.

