#### 852 4.3.2. Participant Selection

853

854 See Section 4. for general eligibility criteria. Further details of inclusion and exclusion 855 criteria for potential LDLT donors are given below.

856

#### **Inclusion Criteria:** 857

858

859 1. LDLT Donors: Following the formal donor evaluation, the decision to perform the donor surgery is entirely at the discretion of the transplant center and the donor. Once 860 861 a donor is accepted into the donor cohort, s/he will be asked for consent to participate 862 in the study of donor long-term outcomes, morbidity and quality of life.

863 2. LDLT Donor Controls: Some potential donors who fail to donate will become 864 controls for the long-term donor study. LDLT donor controls will also be asked to 865 consent to study their long-term outcomes. Failure to donate and subsequent 866 inclusion in the donor control cohort can be based upon recipient issues (condition worsening or availability of DDLT) or donor health issues. In the latter case, the 867 donors may have mild to moderate medical conditions that precluded donation, but 868 which are not expected to impact their long-term quality of life or alter the potential 869 870 donor's natural history of survival/disease development compared to the normal 871 population. We will also utilize donor candidates from the Retrospective Study who 872 have not donated as donor controls.

- 873 a. Assessment of donor controls will be limited to collection of morbidity and 874 survival information, administration of Quality of Life and Informed Consent 875 instruments post-donation. 876 3. The event that will switch a donor from the pre-donation assessment regimen to the 877 donor post-donation assessment regimen or the donor control post-event assessment 878 regimen is the occurrence of one of the following events (whichever happens first): 879 a. Donation 880 b. Donor ruled out (but only with mild co-morbid conditions as outlined above) 881 c. Donor withdraws 882 d. Recipient dies e. Recipient is removed from the waiting list 883 884 f. Recipient receives DDLT 885 886 **Exclusion Criteria:** 887

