#### 1095 4.4.5. Statistical Analysis

1096 The data for this aim will include the Keris modules on comprehension and

1097 understanding, motivation for decision-making, and satisfaction with treatment. Initial

- analyses will provide descriptive statistics on all modules, particularly comprehension
   and understanding, and satisfaction with treatment. Because the ethical nature of
- and understanding, and satisfaction with treatment. Because the ethical nature of informed consent relies on comprehension of the risks involved, low scores on the
- 1101 comprehension questions would bring into question the adequacy of the consent process.

1102 Levels of patient satisfaction with treatment will be of interest to all participating centers,1103 whose programs depend on good patient care.

1104

The first hypothesis involves predictors of the decision to donate. We will use logistic regression to investigate variables potentially predictive of donation. Demographic variables will be included to adjust for any confounding. The primary variables of interest are questions related to sense of duty and need to perform a moral good. Also of interest is whether the level of comprehension and understanding of the information presented is predictive of the decision to donate.

1111

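### Aim 4 asks who donates rather than withdraws, but its model and its 87% power pool withdrawers with candidates who were ruled out or blocked by recipient events

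*Protocol*

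**What the plan says.** Section 4.4 expects certain personal characteristics, such as a strong sense of duty, in people who go through to donation compared "to those individuals that enter the process but withdraw". Objective 3 in section 3.4 likewise concerns the choice between proceeding and withdrawing.

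Section 4.4.4 sizes this hypothesis on all "potential donors in the Cohort Study, assumed to be 360 donors + 710 donor controls", 1,070 in total. The calculation is "Based on logistic regression with significance level 0.05 and 2-sided tests, we" "will have 87% power to detect a difference between a 30% donation rate at the mean" "level of, say, the sense of duty scale, and a 35% donation one standard deviation above" the mean. Section 4.4.5 introduces the hypothesis as one about the decision to donate, then plans logistic "regression to investigate variables potentially predictive of donation".

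Section 4.3.2 says who the controls are: "inclusion in the donor control cohort can be based upon recipient issues (condition" worsening, or a deceased donor organ becoming available) or on donor health. Apart from donation itself (event a), it lists five events that can end an evaluation: donor ruled out (b), donor withdraws (c), recipient dies (d), recipient removed from the list (e), recipient receives DDLT (f). In section 4.4.1 the motivation questions go separately to voluntary withdrawers, to those excluded for medical reasons, and to those whose recipient was transplanted, delisted or died.

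**The concern.** Of the five ways to become a control, only event c is plainly the candidate's own decision. Someone approved and willing, whose recipient then received a deceased donor graft, is a non-event in the model exactly like someone who changed their mind. The outcome analysed is therefore not the one in the hypothesis.

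If the other exits have nothing to do with sense of duty, moral obligation or comprehension, mixing them in pulls the association toward the null. A null result could then be read as evidence that motivation and understanding do not affect the decision, when it partly reflects who was medically or logistically able to donate. The power statement has the matching problem: it describes the pooled outcome, while the reader takes it as the power for the hypothesis.

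**Working it through.** **Inputs from the protocol.** 360 donors, 710 controls, two-sided alpha 0.05, 30% donation at the mean of the predictor and 35% at +1 SD, correlation 0.05 with control variables (all 4.4.4).

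**Input not in the protocol.** w, the share of the 710 controls who withdrew voluntarily. It is varied as an assumption.

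**Step 1: the plan's own figure.** The log odds ratio per SD is b = ln[(0.35/0.65)/(0.30/0.70)] = 0.228, so OR = 1.256. Hsieh's 1989 formula for one continuous covariate, with n multiplied by (1 − R²) and the 0.05 read as R², is

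power = Φ{[√(n(1 − R²)·p·b²/(1 + 2pδ)) − 1.96]/exp(−b²/4)}, with δ = [1 + (1 + b²)exp(5b²/4)]/[1 + exp(−b²/4)].

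With n = 1,070, p = 0.30, R² = 0.05 and δ = 1.068, the square root is 3.11 and power is 87.8%. If 0.05 is instead read as a correlation (R² = 0.0025), power is 89.3%. The stated 87% is reproduced, for donation yes/no in all 1,070.

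**Step 2: what pooling does to the effect.** Assume OR 1.256 applies to donating versus withdrawing.

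*Scenario A: other exits unrelated to the score and to the decision.* Let W = 710w, let q = 360/(360 + W) be the donor share among deciders, and s = (360 + W)/1,070 the share of candidates who reach a decision. The pooled donation probability is s·q, so the slope on the logit scale becomes b(1 − q)/(1 − sq). The fraction of b kept is

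f = [W/(360 + W)]/(710/1,070).

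Example, w = 25%: W = 177.5, so f = 0.330/0.664 = 0.50.

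*Scenario B: every blocked candidate was willing.* The same argument gives (710w/1,070)/(710/1,070) = w, so the fraction kept is w itself.

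**Step 3: power on one formula.** For both contrasts I use Hsieh's 1998 form, Φ[√(n(1 − R²)p(1 − p))·β − 1.96], with R² = 0.05. It is symmetric in events and non-events, which matters because donors are the majority of the restricted set at low w. It is more generous than the 1989 form: with the full effect it gives 91.5% for the plan's case at p = 0.30, and 93.0% at p = 360/1,070. The columns below should therefore be compared with each other and not with 87%. The pooled column uses p = 360/1,070.

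| w | f (A) | pooled OR (A) | pooled power (A), n = 1,070 | donors + withdrawers | restricted power, OR 1.256 | pooled OR (B) |
|---|---|---|---|---|---|---|
| 10% | 0.25 | 1.06 | 13% | 431 | 40% | 1.02 |
| 25% | 0.50 | 1.12 | 40% | 538 | 68% | 1.06 |
| 50% | 0.75 | 1.19 | 73% | 715 | 84% | 1.12 |
| 75% | 0.90 | 1.23 | 87% | 892 | 90% | 1.19 |
| 90% | 0.96 | 1.25 | 91% | 999 | 92% | 1.23 |

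A simulation with 1,000 replicates per setting agrees. At w = 50% the mean fitted slope was 0.169 under A and 0.116 under B. The restricted analysis gave 0.228 and 0.233, against a true 0.228.

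**Step 4: does the larger sample compensate?** Under A the ratio of restricted to pooled test signal is √[(1 − 360/1,070)/(1 − q)]. Since q is never below 360/1,070, this ratio is never below 1. The extra non-donors add no power for the stated hypothesis at any w.

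**The case against.** - **The 87% is correct for what it describes.** Section 4.4.4 defines the effect as a donation rate among all potential donors, and 30% is close to 360/1,070 = 34%. Applying OR 1.256 to donors versus withdrawers is an assumption of this review. This stands: there is no arithmetic error in the 87%.
- **A reader might infer that the dilution is necessarily strong, or that 87% is out of reach for either contrast.** The protocol does not support that, because it gives no withdrawal share. Under scenario A, three quarters voluntary withdrawal costs only about 10% of the log odds ratio. By the 1998 formula the restricted contrast passes 87% once w is about 58%.
- **A reader might infer that blocked candidates are labelled as refusers, or that predictors of medical rule-out will pass for predictors of the decision.** Neither is shown. The modelled outcome is called donation, and objective 2 in section 3.4 speaks of a predisposition to proceed to donation. Section 4.4.5 adjusts for demographics and its variables of interest are motivational. Section 4.3.2 keeps candidates with serious health conditions out of the control cohort.
- **Some other exits may be linked to hesitation.** A slow or reluctant candidate may leave time for the recipient to die or be transplanted, and nothing in the protocol excludes this. Simply dropping events b, d, e and f could then introduce selection. This stands, and it shapes the fix.

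None of these points removes the mismatch between the contrast in 4.4 and the outcome in 4.4.4 and 4.4.5.

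**Conclusion.** The concern holds as a mismatch between hypothesis and outcome, and it rests on the protocol's own text. The direction of the effect, toward the null, follows if the other exits are unrelated to the motivation score or come from willing candidates. Its size cannot be fixed from the protocol. Under scenario A the log odds ratio loses about 75% at w = 10%, 50% at 25%, 25% at 50% and 10% at 75%; under scenario B it loses 1 − w. These figures assume a true OR of 1.256 per SD for donating versus withdrawing.

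The 87% stands for pooled donation yes/no. It should not be read as the power to distinguish donors from withdrawers. This should be fixed, since it affects the first hypothesis of a primary aim. It is short of essential: the exit reasons are already distinguished, so the right analysis remains possible until the data are analysed.

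**What to change.** In 4.4.5, name donated versus voluntarily withdrew (event c) as the primary contrast for the first hypothesis. Fit a multinomial model with three outcomes: donated, voluntarily withdrew, and not able to donate (events b, d, e, f). Excluding the third group is an acceptable alternative. In either case keep the pooled donation model as a sensitivity analysis, because some of those exits may be related to hesitation.

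In 4.4.4, say that 87% applies to donation yes/no in all 1,070. Add the power for 360 donors plus the expected number of withdrawers over a stated range of w: for OR 1.256 per SD, roughly 40% at 10%, 68% at 25%, 84% at 50% and 90% at 75%.

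The cost is analysis wording and a second power statement, which may be less favourable depending on w. No new data collection is needed, since 4.3.2 and 4.4.1 already separate the reasons for not donating.

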#### 1095 4.4.5. Statistical Analysis

1096 The data for this aim will include the Keris modules on comprehension and

1097 understanding, motivation for decision-making, and satisfaction with treatment. Initial

- analyses will provide descriptive statistics on all modules, particularly comprehension
   and understanding, and satisfaction with treatment. Because the ethical nature of
- and understanding, and satisfaction with treatment. Because the ethical nature of informed consent relies on comprehension of the risks involved, low scores on the
- 1101 comprehension questions would bring into question the adequacy of the consent process.

1102 Levels of patient satisfaction with treatment will be of interest to all participating centers,1103 whose programs depend on good patient care.

1104

The first hypothesis involves predictors of the decision to donate. We will use logistic regression to investigate variables potentially predictive of donation. Demographic variables will be included to adjust for any confounding. The primary variables of interest are questions related to sense of duty and need to perform a moral good. Also of interest is whether the level of comprehension and understanding of the information presented is predictive of the decision to donate.

1111

1112 The second hypothesis involves predictors of donor satisfaction with treatment, and will 1113 be restricted to potential donors who actually go through donation after the evaluation 1114 time point. The outcome measure will be a summary of several Likert-scale questions 1115 related to patient satisfaction, and will be a continuous variable for practical purposes. 1116 Linear regression will be used to investigate predictors of patient satisfaction with treatment at each time point from donation. Demographic variables will be included to 1117 adjust for confounding. Several variables are of interest. First we will test variables 1118 1119 related to ease of the post-surgical course (e.g., number and severity of post-surgical 1120 complications, number of days in the hospital). Second we will test variables measuring 1121 the patients' foreknowledge of adverse events that they experienced: we will include in the model both an indicator variable reflecting whether all the patient's adverse events 1122 1123 were listed on the consent form, and also an indicator variable reflecting whether the 1124 patient thought they had been informed of the particular adverse event(s). (It will also be 1125 interesting to see whether patients report not being informed of adverse events that are 1126 given in the consent form, and if so, whether some events are more likely than others to 1127 have been missed by the patient.) Third, we will test variables related to recipient health 1128 for their effect on patient satisfaction with treatment, because one might imagine that the 1129 donor would feel better about donation if the recipient were doing well. Recipient health 1130 will be measured by number and severity of recipient adverse events, recent 1131 hospitalization, liver function tests, and quality of life. Finally, we will test measures of 1132 family acceptance and appreciation based on questions from the A2ALL Donor Survey.

1133

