515	• Quality of life assessment: limited to a pain survey at Week 1 and Month 1 for
516	donors. Donor and donor controls will undergo the full battery of QOL assessments
517	at Months 3, 12 and annually thereafter.
518	• Informed consent assessment (satisfaction with treatment): at Months 1, 3, and 12,
519	and annually thereafter
520	• Informed consent assessment (motivation): at Week 1, Months 3 and 12, and annually
521	thereafter.
522	• Donor controls will be asked to complete the QOL, Informed Consent and data
523	collections. No diagnostic, imaging or invasive procedures will be performed once
524	the decision not to donate has been made.
525	

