#### 920 4.3.5. Statistical Analysis

921 The first goal of the analysis is to estimate the mortality and morbidity after liver

922 donation. Although we expect and hope that no donor mortality occurs, if any does, then

923 probability of mortality will be estimated using the Kaplan-Meier estimator with

924 confidence intervals at specific points such as one and two years. With this estimator, the 925 probability of donor death at any time point during post-surgery follow-up can be given.

926

927 Donor morbidity will be estimated as a proportion of donors with each reported

928 complication at relevant time points after surgery. Complications reported will include

bile leak, primary non-function, graft failure, pneumonia, and urinary tract infection, as

930 well as any complication requiring hospital admission, re-operation, or other intervention.

931 Confidence intervals for each proportion will be given. We will also report follow-up

932 outcomes including wound healing, pain medications, blood laboratory values, and the

proportion of patients who returned to work/school. Some attempt will be made to

correlate complications with patient characteristics and operative procedures, but anysuch analyses will be limited by the quality of available data.

- 936 The second goal of the analysis is to estimate the long-term health-related QOL of donors
- 937 compared to a control population. The analysis will employ repeated measures

938 regression analysis, implemented using SAS Proc Mixed software. Outcome measures

- will be validated scales from established QOL instruments. Mean differences over time
- between donors and controls will be estimated. Possible changing effects over time will
- be tested using time by transplant group interactions. These analyses will be adjusted for
- other variables predictive of health-related QOL, such as age, gender, and baseline
  comorbidities. The covariance structure of the repeated measures over time will be

investigated using a full model prior to any covariate reduction. Donors recruited from
the A2ALL Retrospective Study will initially be analyzed separately, and then compared
with donors from the Cohort Study. If the two donor groups are similar, they may be
pooled to compare with the control group. If the two donor groups are not similar, they

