## 1750 **Pre-transplant, Intraoperative and Post-operative**

1751

Donor and recipient whole blood for genetic repository (24 ml collected at enrollment forrecipients and on the day of donation surgery for the donor)

- 1754 Donor and recipient blood for biorepository (15 ml drawn at enrollment, day of surgery
- and post-transplant day 1, weeks 1 and 2\*, months 1, 3, 6\*, 12 and yearly through month
- 1756 60). Those subjects who have joined the study later in their transplant/donation
- 1757 experience may have blood drawn for the repository at annual visits from Year 5 through
- 1758 Year 10. However, because they will have entered the study after some collection
- timepoints, the total amount of blood drawn from these subjects will be similar to or lessthan that drawn from subjects who entered the study at the time of donor evaluation.
- 1761
- \*Donors will not have blood drawn at week 2 or month 6. Total blood drawn during the
- 1763 five-year study will be 219 ml for donors and a maximum of 304 ml for recipients.
- 1764
- 1765

1766 Additional collection of blood and tissue will be coordinated with other ancillary studies,

1767 and correlated with liver function tests. Revised Cohort Protocol 031006

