#### 2139 Appendix B: Schedule of Donor Visits, Tests and Assessments

\*Donor controls will not have any laboratory, clinical or blood testing performed after decision not to donate has been made. They will continue to be followed

for data collection, QOL and informed consent assessments at the visits listed in the above schedule

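### Donor satisfaction is regressed visit by visit, although it is measured repeatedly in the same donors and the protocol already uses a repeated measures model for their quality of life and pain

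*Protocol*

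**What the plan says.** The second hypothesis of Primary Aim 4 concerns what predicts satisfaction among people who donate. Section 4.4.5 says: "Linear regression will be used to investigate predictors of patient satisfaction with treatment at each time point from donation". It then lists four families of predictors and says that they will be tested ("First we will test variables" opens the list): ease of the post-surgical course, foreknowledge of the adverse events experienced, recipient health, and family acceptance. No primary visit, joint model or significance level is given for this analysis.

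Section 4.4.4 sizes it on "only those potential donors who actually donate, approximately 360 donors", using standard linear regression: "we will have 93% power to detect an increase of 3% in the R"-squared, with five control variables that already explain 10%. A two-sided 0.05 level is stated in that section for the first hypothesis (predictors of donation) and is not repeated for the second.

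The two visit schedules differ. The post-donation list in section 4 has "Informed consent assessment (satisfaction with treatment): at Months 1, 3, and 12" and annually thereafter. In Appendix B the informed consent row is marked after donation only at months 3, 12, 24, 36, 48 and 60, and its footnote follows donor controls "for data collection, QOL and informed consent assessments at the visits listed in the above schedule". Section 4.9.3 describes a "five-year study will be 219 ml for donors and a maximum of 304 ml for recipients", which supports month 60 as the horizon.

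For donor quality of life, section 4.3.5 uses repeated measures "regression analysis, implemented using SAS Proc Mixed software", with time interactions and a planned look at the covariance structure. Pain scores follow the same approach.

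**The concern.** Regression at each visit treats every visit as a separate analysis of the same people. This has three consequences.

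- A predictor with no effect gets six or seven chances to reach significance, and nothing in the section says which visit answers the question.
- An effect that is steady over time is tested each time with one visit's information. Section 4.3.4 itself notes that a repeated measures analysis has more power than a single time point.
- Each regression uses only the donors who responded at that visit, so an apparent change in a predictor's effect over time is mixed with a change in who responded.

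What is at stake is modest but practical. Whether foreknowledge of complications or the recipient's health shapes donor satisfaction bears on how donors are counselled. A scattered pattern of significant visits would be hard to interpret.

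**Working it through.** **Inputs from the protocol.** 360 donors; R-squared increase 0.03; five controls explaining 0.10 (section 4.4.4). Visits: months 1, 3, 12, 24, 36, 48 and 60, which is 7 (section 4), or 6 without month 1 (Appendix B).

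**Assumptions.** Two-sided 0.05 carries over from the first hypothesis. The within-donor correlation ρ of satisfaction between visits is not given, so a range is shown. Correlation is taken as equal between all pairs of visits. For a predictor fixed over time, the visit-specific test statistics then have correlation ρ. This does not hold for predictors that change between visits, such as recipient health.

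**Step 1: the protocol's own power.** Partial F test for one predictor, with error df = 360 − 5 − 1 − 1 = 353.

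f² = 0.03 / (1 − 0.13) = 0.0345; noncentrality = 360 × 0.0345 = 12.4.

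Power = 94.0%. Other common conventions for f² and the noncentrality give 93.3% to 93.7%. The stated 93% reproduces, for one regression at one visit with all 360 donors.

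**Step 2: chance that a null predictor is significant at one visit or more.** With independent tests this is 1 − 0.95^m: 1 − 0.95⁷ = 30.2% and 1 − 0.95⁶ = 26.5%. With equally correlated normal test statistics and the limit |z| > 1.96:

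| ρ | 7 visits | 6 visits |
|---|---|---|
| 0.3 | 27% | 24% |
| 0.5 | 23% | 21% |
| 0.7 | 18% | 16% |
| 0.9 | 11% | 11% |

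**Step 3: power of one joint model for a time-constant effect.** With complete visits, averaging m visits multiplies the noncentrality by m / (1 + (m − 1)ρ). For m = 7 and ρ = 0.5 this is 7 / 4 = 1.75. At the protocol's 3% effect:

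| ρ | Factor, 7 visits | Power, 7 visits | Power, 6 visits |
|---|---|---|---|
| one visit only | 1 | 94.0% | 94.0% |
| 0.5 | 1.75 | 99.6% | 99.6% |
| 0.7 | 1.35 | 98.3% | 98.2% |
| 0.9 | 1.09 | 95.7% | 95.6% |

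The gain over one visit is about 2 to 6 points.

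**Step 4: where the gain is larger.** If only 288 donors (80%, an assumption) respond at a visit, single-visit power for the 3% effect is 88%; with 216 (60%, an assumption) it is 78%. For an effect of 1.5%, a size not in the protocol and used only to illustrate, one visit with all 360 donors gives 69%. Seven visits in one model give 73% at ρ = 0.9, 82% at ρ = 0.7 and 90% at ρ = 0.5.

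**Step 5: keeping separate regressions with a correction.** Bonferroni over seven visits (0.05/7 = 0.0071) lowers per-visit power for the 3% effect to about 78-79%. Over six (0.05/6 = 0.0083) it is about 80-81%.

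**The case against.** The strongest case for leaving the text alone has five parts.

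- **No decision rule is stated.** Section 4.4.5 does not say that any significant visit counts as a positive result, and it gives no level. Each visit's test keeps its own 5%. A multiplicity rule could sit in an analysis plan that is not shown. This stands, and it is why Step 2 is conditional.
- **The wording is partly exploratory.** The section speaks of investigating predictors and of several variables being of interest. That is fair, but the analysis belongs to a primary aim and the predictors are to be tested.
- **Visit-specific effects may be the question.** Complications may matter at month 1 and not at year 5. This stands in part: the gain in Step 3 assumes a constant effect. A joint model with a predictor-by-time term still gives the visit-specific estimates.
- **The contrast with section 4.3.5 is not a contradiction.** That model compares donors with controls over time. For predictors of individual Donor Survey items, the same section also allows ordinary linear or logistic regression. This stands. The comparison shows only that the better method is already in use for these donors.
- **Power is already adequate.** At 3% it is 94% at one visit. This stands.

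A reader might infer that the 93% is wrong, that the plan discards a large amount of power, or that a false-positive rate near 30% is built in. The documents support none of these. The 93% reproduces. The gain at the protocol's own effect is a few points, and larger gains need a smaller effect or missing visits, neither of which the protocol quantifies. The 30% needs independent visits, which is implausible in the same donors.

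**Conclusion.** The point holds as a cheap improvement and not as an error. The protocol fixes a visit-by-visit method for a repeated outcome when a better one is already in its own section 4.3.5.

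Read as any significant visit at 0.05, a null predictor that is fixed over time would appear as a finding with probability about 11-27% (seven visits) or 11-24% (six). This rests on an assumed correlation between 0.9 and 0.3, on a level that is stated only for the first hypothesis, and on a decision rule that the protocol does not state. The efficiency loss at the protocol's effect is about 2-6 points of power for ρ between 0.9 and 0.5, assuming complete visits and a constant effect.

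The number of satisfaction visits is itself inconsistent between section 4 and Appendix B, but the conclusion is the same with six or seven.

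**What to change.** In section 4.4.5, replace the regression at each time point with one repeated measures model per predictor family. Use all available visits and let the recipient-health terms vary over time. Define the primary test as the visit-averaged effect of the predictor. Test predictor-by-time as a secondary question, and report visit-specific estimates with confidence intervals from the same model. State the significance level for this hypothesis.

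In section 4.4.4, label the 93% as the single-visit figure with all 360 donors. Reconcile the month-1 satisfaction assessment between section 4 and Appendix B.

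The cost is wording plus the choice of a covariance structure, which is already planned for quality of life. No new data, donors or visits are needed to change the model. Multiplicity across the four predictor families remains and needs its own rule or an exploratory label.
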